12.3 Investigator’s responsibility for reporting serious adverse events

All SAEs will be reported within 24 hours of the site staff becoming aware of the event. The SAE (Initial) Form will be completed and faxed to the Sponsor on [contact] using all information known at the time. A minimum of the SAE title, onset date and date the last investigational product was delivered should be provided, and if possible, the form should be reviewed and signed by the site investigator prior to faxing.

Further guidance on SAE reporting, including instructions for completion of the SAE form can be found in Study Reference Manual.

If site staff becomes aware of new information regarding an SAE, a SAE (Follow Up) form should be completed and forwarded to the Sponsor within five days. New information may include recurrent episodes, complications, or progression of the initial SAE, acquisition of relevant hospital records, reports and/or laboratory results. The follow-up information should describe whether the event has resolved or continues, if and how it was treated, and whether the patient continued or withdrew from study participation.

SAEs, regardless of suspected causality, occurring after the patient had provided informed consent and until 30 days after the patient has stopped study participation/ withdrawn, must be reported. Any SAEs experienced after this 30 day period should only be reported if the Investigator suspects a causal relationship to the study drug. SAEs that are ongoing at the end of the study should be followed up until a final assessment is possible, and until all queries from the Sponsor have been resolved.

In accordance with local requirements, the site investigator must also notify their local EC of any SAEs.

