8.3 Stopping Rules

Study enrolment may be stopped if death of a participant that is related to the study treatment occurs.

Safety data will be presented by group in a blinded fashion to the Data Safety and Monitoring Board (DSMB) at scheduled DSMB meetings during the trial. The DSMB will have the authority to request un-blinded data if necessary. The DSMB may recommend that enrolment or study treatment be discontinued for the safety of participants.

Resumption of the study will be contingent upon a favourable decision by the Sponsor, and the DSMB after review of the adverse event data.

9. Selection and withdrawal of participants

Deviations from the eligibility criteria will not be permitted as they may potentially jeopardise patient safety and the scientific integrity of the study.

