12.1 Adverse events

In accordance with the TGA GCP guidelines (CPMP/ICH/135/95), an AE is any untoward medical occurrence in a participant administered a medicinal product and which does not necessarily have a causal relationship with this treatment. An AE can therefore be any unfavourable and unintended sign (including an abnormal laboratory finding), symptom, or disease temporally associated with the use of the investigational product, whether or not considered related to the investigational product.

All AE should be well documented in the participant's source notes and CRF. Start and stop dates, outcome and whether the participant required treatment will be recorded. The site investigator will determine the title of the AE, severity, relationship to investigational product and seriousness.

An AE does not include:

- Pre-existing disease or condition that was present prior to the first administration of the investigational product, and that does not have a clinically significant increase in severity and/or frequency during the study
- Medical or surgical procedures. The disease or condition that led to the procedure should be recorded as the AE, not the procedure itself.

AEs will be followed up until they have returned to baseline status or stabilised. Follow-up of AEs should continue until the overall clinical outcome has been ascertained or the final visit completed.

If an AE later escalates to meet the criteria for a SAE (see Section 12.2), then it must be reported to the Sponsor as an SAE. See Section 12.3 for Investigator's responsibilities for reporting SAEs.

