12.2.2 Clarification of serious adverse events

Death is an outcome of an AE and not an AE in itself.

A “life threatening” event is any adverse therapy experience that, in the view of the site investigator, places the participant at immediate risk of death from the reaction as it occurred.

An “inpatient hospitalisation” occurs when a participant is formally admitted to hospital for any length of time. It does not refer to Emergency Department or Accident & Emergency visits where the patient is observed and not admitted.

“Hospital in the home” or equivalent programs are not considered inpatient hospitalisations, and therefore do not need to be recorded as SAE’s.

Hospitalisations considered to be “routine” and therefore not SAEs will include hospitalisation for procedures unrelated to respiratory system or to the trial. Site staff will notify the Sponsor of routine hospitalisations within one week of the admission. Reporting instructions are provided in the Study Reference Manual.

If a routine hospitalization is prolonged due to an AE or results in any of the other definitions in Section 12.2.1, it should be reported to the Sponsor as a SAE.

Medical and scientific judgment should be exercised in deciding whether other situations than those listed in [Section 12.2.1](#) should be considered serious. This may include important medical events that might not be immediately life-threatening or result in death or hospitalization but might jeopardise the participant or might require intervention to prevent one of the other outcomes listed in Section 12.2.1.

Regardless of the relationship of the event to the investigational product, the event must be reported as a SAE if it meets any of the definitions listed in Section 12.2.1.

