12.4 Reporting to regulatory authorities

It is important that all known information at the time of the SAE is forwarded to the Sponsor within the protocol required time frame, as expedited reporting to the appropriate regulatory authorities may be required based on the following criteria:

No Reporting

This requirement applies if the SAE is deemed not serious by the Principal Investigators.

Standard Reporting

This requirement applies if the SAE is classified as any of the following:

- Serious, expected, and related to the investigational product
- Serious, expected and *not* related to the investigational product
- Serious, *unexpected* and *not* related to the investigational product

Expedited Reporting

This requirement applies if the SAE is classified as serious, unexpected and related to the investigational product. During these circumstances, the Sponsor must notify the appropriate health authorities within 15 days, however fatal or life-threatening events must be reported within 7 days.

13. Statistical considerations

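### Section 12.3 allows five days, rather than 24 hours, to tell the sponsor that an already reported SAE has become life-threatening or fatal

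*Combined protocol and SAP*

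**What the plan says.** Section 12.3 sets two site-to-sponsor limits. For the initial report: "All SAEs will be reported within 24 hours of the site staff becoming aware of the event". For later information on an SAE already reported: "a SAE (Follow Up) form should be completed and forwarded to the Sponsor within five days". It then describes what that later information can be: "New information may include recurrent episodes, complications, or progression of the initial SAE", along with hospital records, reports and laboratory results. Nothing in the paragraph separates a change in seriousness from routine updating.

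Three other rules bear on the reading:

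- Section 12.2.2: "Death is an outcome of an AE and not an AE in itself".
- Section 12.2.2, on the general duty to report: "the event must be reported as a SAE if it meets any of the definitions listed in Section 12.2.1".
- Section 12.1, on escalation to an SAE: "If an AE later escalates to meet the criteria for a SAE (see Section 12.2), then it must be reported to the Sponsor as an" (the closing abbreviation is left off here). This addresses an AE that was not serious at first. It does not address an SAE that gets worse.

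Two later steps depend on what the sponsor knows. Under 12.4, for events that are serious, unexpected and related, "fatal or life-threatening events must be reported within 7 days". Under 8.3, "Study enrolment may be stopped if death of a participant that is related to the study treatment occurs". The synopsis lists one other ground for stopping enrolment, a sponsor decision. Section 8.3 also lets the DSMB recommend discontinuation at its discretion.

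**The concern.** Take a worker admitted with a respiratory infection. The admission is an SAE and is reported within 24 hours. The worker later becomes critically ill or dies. Because death is classed as an outcome, and worsening is listed as follow-up information, the natural reading is that the site now has five days. A worker whose death is the first thing reported falls under 24 hours. Two deaths of equal importance thus have different limits, and the longer one applies where a warning event was already on file.

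At stake is the time left for regulatory reporting under 12.4, and how soon the sponsor can learn of a treatment-related death, the only event-specific trigger for a possible enrolment stop. Section 12.4 itself asks that SAE information be forwarded within the protocol's time frame because expedited reporting may follow, so it relies on the limits in 12.3.

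**Working it through.** There is no stated figure to reproduce. The check is a reading of the rules followed by subtraction.

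**Which limit applies**

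| Situation | Rule that covers it | Limit |
|---|---|---|
| Death or life-threatening event is the first SAE report | 12.3, initial report | 24 hours |
| Non-serious AE becomes serious or fatal | 12.1 escalation, then 12.3 initial report | 24 hours |
| Reported SAE later becomes life-threatening or fatal | 12.3 follow-up (progression); 12.2.2 (death is an outcome) | Five days |
| Recurrence or complication that itself meets 12.2.1 | 12.3 follow-up by its list; 12.2.2 general duty plus 12.3 initial report by its definition | Unclear: five days or 24 hours |

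**Inputs.** Initial limit 1 day (12.3); follow-up limit 5 days (12.3); regulatory limit 7 days (12.4); accrual 4 weeks (synopsis).

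**Extra site-to-sponsor time at the maximum:** 5 − 1 = 4 days.

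**Effect on the 7-day limit.** The start of the clock is not stated, so both cases are shown:

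- Clock from site awareness: 7 − 5 = 2 days left on the follow-up route, against 7 − 1 = 6 on the 24-hour route.
- Clock from sponsor receipt: authorities informed by day 5 + 7 = 12 after site awareness, against 1 + 7 = 8.

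**Sensitivity.** The protocol does not say whether the five days are calendar or working days. If they are working days (an assumption), they can span 7 calendar days. The extra time is then 7 − 1 = 6 days, and 7 − 7 = 0 days remain if the 7-day clock is in calendar days from site awareness.

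**Enrolment trigger.** Accrual is planned for 4 × 7 = 28 days, so a 4-day lag is 4/28, or one seventh, of the period in which an enrolment stop can act.

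**After the change.** The maximum falls from 5 days to 1. If the clock runs from site awareness, 6 of the 7 days remain.

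**The case against.** The best reply is that 12.2.2 already settles the matter: anything meeting a seriousness criterion must be reported as an SAE, and all SAEs are due in 24 hours. On that reading the five-day list is for paperwork. This has force for a recurrence or complication that is serious in its own right, so a reader who infers a flat contradiction within 12.3 goes too far; it is an ambiguity. The reply is weaker for worsening of the same SAE. The general duty does not call for a second initial report, and the more specific wording places progression under follow-up.

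Section 12.3 also points to a Study Reference Manual for further guidance. It is not among the documents and may deal with escalated SAEs. The gap can be shown only for the protocol.

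Several stronger inferences are not supported:

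- **That such reports would be late.** A site using all five days would comply. The 4 days are measured against the 24-hour standard, and five days is a ceiling, not an expected delay.
- **That the delay can be turned into a count of avoidable doses.** The 8.3 trigger is permissive and concerns enrolment, not dosing, and no section says dosing would pause on notice of one death. While enrolment is open the initial-treatment group is still filling, and the wait-list group starts treatment only in Month 3, after planned accrual.
- **That all deaths relevant to 12.4 are affected.** The 7-day limit covers only unexpected, related events, and only those that turned fatal or life-threatening after an SAE report are delayed.
- **That this is the typical course of a fatal respiratory event here.** The documents give no figure for how often an admission precedes a death.

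The 12.3 list does not mention causality. That a later change in relationship would also travel as follow-up information is an inference. It is a reasonable one, because the minimum content of the initial form (title, onset date, date of last product) does not include relationship.

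**Conclusion.** The point stands as a specific gap in the safety-reporting rules. As written, the protocol lets up to five days pass before the sponsor learns that a reported SAE has become life-threatening or fatal, 4 days more than for a first-reported event of the same gravity. For unexpected and related cases this means 2 rather than 6 days left, or day 12 rather than day 8, depending on a clock start the protocol does not give. Neither case makes the 7-day limit unattainable if the five days are calendar days.

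It can also delay sponsor knowledge of a treatment-related death during a planned 4-week accrual. The affected cases there are few: dosing, a reported SAE and a later related death must all occur before enrolment closes. For recurrences and complications that meet 12.2.1, the fault is that a site cannot tell which limit applies.

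The conclusion rests on the protocol text alone and on the five-day limit being used in full.

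**What to change.** In section 12.3, keep five days for records, laboratory results and routine updates, and add a sentence to this effect: *Follow-up information that makes a reported SAE fatal or life-threatening, that changes its relationship to Possibly or Probably, or that describes a recurrence or complication itself meeting Section 12.2.1, is reported to the Sponsor within 24 hours of site awareness.* Qualify the list of new information so that it no longer places those cases under five days.

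Two small clarifications would remove the ranges shown above: whether the five days are calendar or working days, and when the 7-day clock in 12.4 starts. The SAE form instructions and the Study Reference Manual should be brought into line.

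The cost is a sentence in the protocol and the matching form instructions, with a few forms sent sooner. No visits, samples or data items are added.

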12.4 Reporting to regulatory authorities

It is important that all known information at the time of the SAE is forwarded to the Sponsor within the protocol required time frame, as expedited reporting to the appropriate regulatory authorities may be required based on the following criteria:

No Reporting

This requirement applies if the SAE is deemed not serious by the Principal Investigators.

Standard Reporting

This requirement applies if the SAE is classified as any of the following:

- Serious, expected, and related to the investigational product
- Serious, expected and *not* related to the investigational product
- Serious, *unexpected* and *not* related to the investigational product

Expedited Reporting

This requirement applies if the SAE is classified as serious, unexpected and related to the investigational product. During these circumstances, the Sponsor must notify the appropriate health authorities within 15 days, however fatal or life-threatening events must be reported within 7 days.

13. Statistical considerations

13.1 Randomisation, stratification and blinding

Participants will be randomised to the wait list group (Group 1) or the initial intervention group (Group 2) using a one-to-one ratio, stratified by Country (Australia, UK), hospital (QCH, PA, TPC) and department [High risk (ED, ICU, isolation wards), lower risk (radiology, general wards, other)].

13.2 Sample size calculations

There are no data in the literature on use of OM85 for the primary prevention of ARI, in relation to COV. However, 20% of Italy's HCW are infected with COV¹. If we assume 20% infection in Gp 1, then with 500 HCW in each group we will be able to detect a reduction in ARI in Gp 2 by 32.5% (to 13.5%) with 80% power ($\alpha=0.05$). Combined with 1000 UK-recruited HCW, we will be able to detect a 25% reduction (80% power, $\alpha=0.05$).

13.2.1 Analysis sample

All participants randomised who receive at least one dose of study treatment will be included in the "intention-to-treat" group for statistical analyses.

Participants who complete the treatment period and take at least 80% of scheduled doses will be included in the "per protocol" group for statistical analyses.

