8.1 Description

This study will be conducted as a multi-centre, parallel group, wait list design clinical trial testing the reduction of acute severe respiratory events requiring workforce removal in HCW with OM85. Health Care Workers who are eligible will receive daily OM85 for 3 months. Group 1 “Wait-list group” will be given daily OM85 for 3 months commencing in Month 3, with 3 months follow-up off treatment. Group 2 “Initial treatment group” will be given daily OM85 for 3 months commencing in on day 0, with 3 months follow-up off treatment

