10.2 Scheduled visits

This study consists of 5 visits (Group 1 - WLC) or 4 visits (Group 2 – initial treatment) over 6 or 9 months respectively (see Figure 1) Study procedures to be performed at each visit are detailed in the Schedule of Assessments and Procedures in Appendix 1.

Visits should be conducted within the specified visit windows where possible.

Figure 1: Study timeline and procedures. Nasal swab collection (blue arrow), blood collection (red arrow).

Group 1 (WLC)

Visit 1 – Screening and randomisation

The following assessments and procedures will be performed and recorded at this visit:

- Obtain written informed consent
- Evaluate inclusion and exclusion criteria
- Obtain demographic history
- Obtain medical history
- Vital signs
- Explain daily respiratory symptom data collection and assist with collection for Day 0

Once all screening procedures have been completed and eligibility confirmed, the participant will be registered with the Sponsor. Further information on the registration process is provided in the Study Reference Manual.

Visit 2: Treatment initiation 3 months post randomisation (±5 days)

- Update demographic & medical history
- Vital signs

- Nasal swab
- Collection of blood samples
- Dispense study medication and explain administration
- Adverse event assessment

Visit 3: Treatment cessation 6 months post randomisation (± 5 days)

- Vital signs
- Nasal swab
- Collection of blood samples
- Clarify any missing data (daily respiratory symptoms) with participant, if not previously addressed by email/SMS
- Adverse event assessment
- Collect used investigational product packaging and unused investigational product

Visit 4: Follow up cessation 9 months post randomisation (± 5 days)

- Vital signs
- Nasal swab
- Collection of blood samples
- Clarify any missing data (daily respiratory symptoms) with participant, if not previously addressed by email/SMS
- Adverse event assessment

Unscheduled Visit: at time of ARI necessitating workforce removal

- Vital signs
- Nasal swab
- Collection of blood samples
- Clarify any missing data (daily respiratory symptoms) with participant, if not previously addressed by email/SMS
- Adverse event assessment

Group 2 (Initial Treatment)

Visit 1 – Screening, randomisation, and treatment initiation

The following assessments and procedures will be performed and recorded at this visit:

- Obtain written informed consent
- Evaluate inclusion and exclusion criteria
- Obtain demographic history

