11.1 Enrolment and randomisation

Once all required screening assessments are completed and eligibility is confirmed, participants will be registered with the Sponsor. Upon approval of registration, participants will be assigned a unique participant number that will remain consistent for the duration of the study.

Participants who sign an informed consent form, but do not fulfil the inclusion/exclusion criteria, will not be allocated a participant identification number.

Participants will be randomised into one of the following two groups on a 1:1 ratio with 500 participants per group:

- Group 1 (WLC): OM85 7.0 mg will be given daily for three months from Month 3
- Group B (Initial Treatment): OM85 7.0 mg will be given daily for three months from Day 0

Please see the Study Reference Manual for randomisation instructions.

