13.2.2 Statistical analyses

The *interim analysis*, undertaken at month 1 on both the "intention-to-treat" and "per protocol" groups, will examine the primary outcome: if the treatment difference is statistically significant in favour of OM85 the DSMB will consider immediately switching WLC participants to OM85.

Between-group differences in the primary outcome at 3 months will be assessed using log-binomial regression. Secondary outcomes measured to follow-up cessation will be assessed using mixed-effects models with group and stage (treatment/follow-up) (main effects and interaction) as fixed effects and HCW as random effect. Time-to-ARI analyses will use the log-rank test. Analyses will be undertaken on both the "intention-to-treat" and "per protocol" groups.

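### Both analysis sets are defined by OM85 doses that wait-list controls do not take before month 3, so the month-1 and month-3 comparisons lack a usable rule for who is a control

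*Combined protocol and SAP*

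**What the plan says.** Section 13.2.1 (Analysis sample) gives two sets. For ITT: "All participants randomised who receive at least one dose of study treatment will be included in the" intention-to-treat group. For per protocol: "Participants who complete the treatment period and take at least 80% of scheduled doses will be included in the" per-protocol group.

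OM85 is the only study treatment, and no placebo is described. Section 11.1 states "Group 1 (WLC): OM85 7.0 mg will be given daily for three months from Month 3". Section 10.2 and Appendix 1 place the wait-list start at day 90 and the end of treatment at day 180, each within 5 days. Group 2 starts on day 0 and stops at day 90.

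Section 13.2.2 has an interim analysis of the primary outcome "undertaken at month 1 on both the" ITT and per-protocol sets. Section 13.3.1 runs the primary analysis at 3 months on the same two sets, using data from before the wait-list group starts treatment. Sections 13.2.2 and 13.3.2 also use both sets for the secondary outcomes measured through follow-up cessation, and 13.3.2 does so for the mechanistic evaluations.

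The sample size in 13.2 treats Group 1 as a full comparator: "If we assume 20% infection in Gp 1, then with 500 HCW in each group".

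**The concern.** A set defined by dosing suits a placebo-controlled trial, where both arms have something to take from day 0. Here the control arm has nothing to take until its outcome window for the primary comparison has closed. Applied literally, the definitions remove the controls or admit them through something they do later.

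The rule for who counts as a control in the primary comparison therefore cannot be applied as written, and the analyst has to supply one. All randomised controls and only those controls who later started OM85 are different populations. The second is selected by an event after the outcome window, while Group 2 members qualify on day 0. If starting OM85 depends on having had an ARI, that comparison is biased. Settling the rule after outcomes are known would weaken the primary result whichever rule was chosen.

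**Working it through.** **1. The plan's own power figure.** Inputs from 13.2: 20% in Group 1; 13.5% in Group 2 with 500 per group, or a 25% reduction (to 15%) with 1000 per group; alpha 0.05, taken as two-sided. Power = Φ[(|p1 − p2| − 1.96·s0)/s1], with s0 the pooled and s1 the unpooled standard error.

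- 500 per group: s0 = √(0.1675 × 0.8325 × 2/500) = 0.02362; s1 = 0.02353; (0.065 − 0.0463)/0.02353 = 0.795; power 78.7%.
- 1000 per group: s0 = 0.01699; s1 = 0.01696; (0.05 − 0.0333)/0.01696 = 0.985; power 83.8%.

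Both are close enough to the stated 80%. The sample-size arithmetic is not at issue. It assumes every randomised control is analysed.

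**2. Who is in each set when each analysis is run.** Accrual takes 4 weeks (synopsis). At month 1 after accrual closes, the longest time on study is 28 + 30 = 58 days. At month 3 for the last enrollee, it is 28 + 90 = 118 days. The earliest wait-list first dose is day 90 − 5 = 85, and the earliest end of wait-list treatment is day 180 − 5 = 175.

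| Analysis | Set | Controls | Group 2 |
|---|---|---|---|
| Month 1 | ITT | 0 (58 < 85) | those dosed |
| Month 1 | Per protocol | 0 | 0 (58 < 85, the earliest end of treatment) |
| Month 3 | ITT | 0, or only later starters | those dosed |
| Month 3 | Per protocol | 0 (118 < 175) | completers with 80% of doses |

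Month-3 ITT is ambiguous because 13.2.1 sets no deadline for the first dose and 13.3.1 restricts the data, not membership. If membership is judged on data from before wait-list treatment, there are no controls. If later doses count, only starters enter. On calendar day 118, Visit 2 has come round for all controls if held at day 90, and for (118 − 95)/28 = 82% if all are held at day 95 (uniform accrual assumed).

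If membership were instead fixed at study completion, controls could enter either set, but only through what they did after their outcome window.

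**3. Does another section admit undosed controls?** Section 9.3.1 places in ITT those who stop the product but continue to be assessed; it does not cover people who have not started. Section 13.3.3 includes all participants, for safety only. Reading the scheduled doses as zero for controls does not help, because per protocol still requires a completed treatment period and none is defined for controls in months 0 to 3.

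**4. Illustration for month-3 ITT limited to later starters.** Assumed: no drug effect, 20% risk in both arms, Group 2 kept whole, and starting rates a (controls with an ARI) and b (controls without). Included controls N = n(0.20a + 0.80b). Their observed risk = 0.20a/(0.20a + 0.80b). Error is the two-sided rejection rate of the test in step 1.

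Example, a = 0.85, b = 0.95, n = 500: N = 500 × 0.93 = 465; risk = 0.17/0.93 = 18.3%; difference 0.0172; s0 = 0.02536; s1 = 0.02532. The tails are 0.100 and 0.004, so error is 10.4%.

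| a vs b | Control risk | RR (Group 2 / controls) | Error, 500 / 1000 per group |
|---|---|---|---|
| 90 vs 90 | 20.0% | 1.00 | 5.0% / 5.0% |
| 90 vs 95 | 19.1% | 1.04 | 6.3% / 7.6% |
| 95 vs 90 | 20.9% | 0.96 | 6.3% / 7.7% |
| 85 vs 95 | 18.3% | 1.09 | 10.4% / 16.0% |
| 95 vs 85 | 21.8% | 0.92 | 10.7% / 16.5% |

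A neutral loss of 10% of controls (450 or 900 remain) lowers power from 78.7% to 76.6% and from 83.8% to 81.8%.

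**The case against.** The strongest reply is that the intent is obvious. Sections 13.2, 13.2.2 and 13.3.1 all presuppose a Group 1 comparator before its treatment, and an analysis with no controls cannot be run, so the literal reading would be noticed at once. That stands as to intent: all randomised controls, as allocated, is the likely meaning. It does not supply the missing rule. It also leaves the less visible reading available, in which controls enter ITT by later starting OM85.

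The month-3 per-protocol zero is conditional. Section 13.2.1 sets no time limit on completing treatment, and section 13.3 also plans analyses at study completion. The zero assumes that membership is fixed when the 3-month analysis is run. That is the natural reading of 13.3 and 13.3.1, but it is a reading.

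The error rates rest on assumed starting rates and filter one arm only. As written, ITT would also drop any Group 2 member who never took a dose. If the same filter by ARI status applied in both arms, both observed risks would move together and error would return to 5%. The table is an illustration, not an estimate.

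A reader might infer from section 10.3, which excepts ARI with workforce removal from the reasons for an early withdrawal visit, that controls with an event will leave before starting OM85. The wording makes that conceivable but gives no rate and does not establish it.

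**Conclusion.** The definitions in 13.2.1 are wrong as written and must be corrected. Three of the four set-by-timepoint comparisons have no controls, and one of those three has no participants at all. The fourth has none, or only controls selected by an event after their outcome window. These counts assume membership is fixed when each analysis is run. They depend on no assumption about behaviour, and they are what the conclusion rests on.

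The size of any bias is unknown. Under the assumed gaps, error runs from 5% (no gap) through about 6% / 8% (5 points) to 10–11% / 16–17% (10 points). Neutral loss of a tenth of controls costs about 2 points of power.

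Three stronger readings are not supported. First, that the primary result will be biased, or biased in favour of OM85: the documents do not show whether starting OM85 depends on ARI, or in which direction. Second, that adherence filtering distorts the written month-3 per-protocol result: with no controls in that set there is no comparison to distort. Third, that the month-1 switch decision would be wrong by some amount: nothing here models month 1.

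**What to change.** In 13.2.1, define ITT as all randomised participants, analysed as allocated whether or not they ever take OM85. Name it the primary set for the month-1 and month-3 comparisons.

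Make per protocol supportive and define it by stage:

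- **Comparisons before wait-list treatment starts.** Group 1: no OM85 before the scheduled start. Group 2: at least 80% of the doses due to date. State that this filters almost only Group 2, within its outcome window, and so remains open to selection bias.
- **Secondary and mechanistic analyses through follow-up cessation.** Keep the existing rule (treatment period completed, at least 80% of doses) for each group's own treatment stage. A single rule covering only the first 3 months would ignore Group 1's adherence while it is on OM85.

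Edit 13.2.2, 13.3.1 and 13.3.2 to match, before any between-group comparison is made. The cost is wording in those four sections; no extra participants or data are needed.
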